Study Protocol

Title: The Role of Oral Verapamil in Preventing Radial Spasm During Transradial Angiography

ClinicalTrials.gov Identifier: NCT06447688

Sponsor / Responsible Party: Mersin Medicalpark Hospital/ [name]

IRB Approval: Mustafa Kemal University Ethics Committee, No: 2022/102

Version Date: 24.10.2022

1. Background and Rationale

Radial artery spasm (RAS) is the most frequent complication of transradial access (TRA) for coronary angiography and interventions. It can cause severe patient discomfort, technical difficulties, and procedural failure. The reported incidence of RAS ranges from 4% to 51%. Preventing spasm is more effective than treating it once it occurs.

Hypothesis: Oral administration of 120 mg verapamil before the procedure reduces the incidence of RAS.

2. Objectives

- **Primary Objective:** To evaluate the effect of oral verapamil on the incidence of clinical and ultrasonographically confirmed radial artery spasm.
- **Secondary Objectives:**
 - To assess the procedural success rate
 - To evaluate contrast volume, fluoroscopy time, and radiation dose

3. Study Design

- **Type:** Prospective, randomized, placebo-controlled clinical trial
- **Location:** Medicalpark Mersin Hospital, Turkey
- **Enrollment Period:** June 2024 – November 2024
- **Sample Size:** 150 participants (75 per group)
- **Randomization:** 1:1 block randomization

4. Participants

Inclusion Criteria:

- Adults scheduled for coronary angiography via radial approach

Exclusion Criteria:

- Abnormal Allen test
- Absent radial pulse
- Previous radial procedure on the same arm
- Hemodynamic instability
- Contraindications to verapamil (e.g., AV block, EF <35%, severe aortic stenosis)

5. Interventions

- **Experimental Group:** 120 mg oral verapamil, 2 hours before procedure
- **Control Group:** Placebo, same schedule

6. Procedures

- Local anesthesia with 2% prilocaine
- Radial puncture using 20 20-G needle
- 6F hydrophilic sheath insertion
- Intra-arterial heparin 5000 IU
- No routine intra-arterial vasodilators are used
- Coronary angiography performed with 6F Judkins catheters
- PCI performed if indicated, with additional weight-adjusted heparin
- Hemostasis with TR Band (patent hemostasis technique)

7. Endpoints

Primary Endpoints:

1. Clinical RAS incidence (≥ 2 of: forearm pain $\geq 4/10$, pain during catheter manipulation, catheter restriction, pain during sheath removal, difficulty with sheath removal)
2. Ultrasonographic RAS ($\geq 50\%$ lumen narrowing)

Secondary Endpoints:

- Procedural success
- Contrast volume (mL)
- Fluoroscopy time (minutes)
- Radiation dose (DAP, mGy·cm²)

8. Statistical Considerations

- Sample size: 150 (75 per arm), calculated with 80% power and $\alpha=0.05$
- Normality test: Shapiro–Wilk
- Parametric variables: Student t-test
- Non-parametric: Mann–Whitney U
- Categorical: Chi-square or Fisher exact
- Predictors: Logistic regression

9. Ethics

- Conducted in accordance with the Declaration of Helsinki
- Approved by Mustafa Kemal University Ethics Committee (2022/102)
- Written informed consent obtained from all participants

10. Amendments

No protocol amendments occurred during the study period.

Statistical Analysis Plan (SAP)

Title: The Role of Oral Verapamil in Preventing Radial Spasm During Transradial Angiography

ClinicalTrials.gov Identifier: NCT06447688

Sponsor / Responsible Party: Mersin Medicalpark Hospital/ [name]

IRB Approval: Mustafa Kemal University Ethics Committee, No: 2022/102

Version Date: 24.10.2022

1. Objectives

- **Primary Objective:**

To evaluate the effect of oral verapamil (120 mg, administered 2 hours before procedure) on the incidence of clinical and ultrasonographically confirmed radial artery spasm (RAS).

- **Secondary Objectives:**

- To assess procedural success
- To compare fluoroscopy time (minutes)
- To compare contrast volume (mL)
- To compare the radiation dose (DAP, mGy·cm²) between groups

2. Analysis Populations

- **Intent-to-Treat (ITT):** All randomized participants (N=150; 75 per arm) included in the final analyses.
- **Per-Protocol (PP):** Same as ITT since no participants were excluded or dropped out.

3. Sample Size Determination

- Assumptions: RAS incidence 20% in placebo group vs. 5% in verapamil group
- Power: 80%
- Alpha: 0.05 (two-sided)
- Required sample size: 150 participants (75 per arm)
- Software: PASS 11.0

4. Statistical Methods

- **Descriptive Statistics:**
 - Continuous variables: mean \pm SD if normally distributed; median (IQR) if not
 - Categorical variables: counts and percentages
- **Comparative Analyses:**
 - **Normality:** Assessed with the Shapiro–Wilk test
 - **Continuous variables:** Student’s t-test (parametric), Mann–Whitney U test (non-parametric)
 - **Categorical variables:** Chi-square test or Fisher’s exact test, as appropriate
- **Regression Analyses:**
 - Logistic regression was performed to identify independent predictors of RAS
 - Variables considered: age, sex, comorbidities, procedural factors
 - Results presented as odds ratios (OR) with 95% confidence intervals (CI)
- **Significance Threshold:**
 - Two-tailed $p < 0.05$ is considered statistically significant

5. Handling of Missing Data

- No missing outcome data anticipated (all 150 completed the study)
- In the event of missing data, analysis would proceed with available cases; no imputation planned

6. Subgroup and Sensitivity Analyses

- No predefined subgroup analyses
- Sensitivity analyses are not required due to full completion of the study

7. Software

- Data entry and analyses performed using **SPSS version 25.0 (IBM Corp, Armonk, NY, USA)**

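### Two primary endpoints with no rule for combining them, and a sample size built on one unlabelled RAS rate: the stated alpha of 0.05 and 80% power hold together only for one endpoint tested once

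*Combined protocol and SAP*

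**What the plan says.** - Protocol 1 (hypothesis): verapamil "reduces the incidence of RAS". RAS is one undivided term here.
- Protocol 2 and SAP 1 (primary objective): in the Protocol's words, "To evaluate the effect of oral verapamil on the incidence of clinical and ultrasonographically confirmed radial artery spasm".
- Protocol 7: two separately numbered primary endpoints. The first is "Clinical RAS incidence", met by at least two of five pain and catheter- or sheath-handling signs. The second is "Ultrasonographic RAS", met by lumen narrowing of at least 50%.
- SAP 3: "Assumptions: RAS incidence 20% in placebo group vs. 5% in verapamil group", with 80% power, two-sided alpha 0.05 and 75 per arm. The definition of RAS is not given.
- SAP 4: categorical variables are compared by chi-square or Fisher's "exact test, as appropriate", and a two-tailed p below 0.05 "is considered statistically significant".

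Neither document says whether one or both primary endpoints must succeed, ranks them, or divides or adjusts alpha.

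**The concern.** One definition rests mainly on pain and handling signs and the other on imaging, so a patient can meet one and not the other, and the two comparisons can disagree. If one is significant and the other is not, the documents cannot say whether the trial succeeded. The success criterion could then be settled after the results are seen.

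The missing rule also decides what the stated error rates mean. Letting either endpoint carry the claim affects alpha and does not reduce power. Requiring both affects power and does not inflate alpha.

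**Working it through.** **Inputs from the documents.** 75 per arm, 20% versus 5%, two-sided 0.05, 80% power (SAP 3); chi-square or Fisher (SAP 4).

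**Assumptions, because the documents give no figure.** The correlation r between the two test statistics is 0 to 0.9. Both definitions run at 20% versus 5% unless stated otherwise.

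**1. The plan's own figure.** With pooled proportion 0.125, n per arm = [1.96·√(2·0.125·0.875) + 0.842·√(0.20·0.80 + 0.05·0.95)]² / 0.15² = (0.917 + 0.383)² / 0.0225 ≈ 75.1, which rounds up to 76. At 75 per arm the power is 79.9% by this approximation. Enumerating all outcome tables gives 82.7% for uncorrected chi-square and 76.0% for Fisher. The stated figure therefore fits one binary endpoint tested once.

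**2. Either endpoint may carry the claim, each at 0.05.** Under no effect, with (Z1, Z2) bivariate normal with correlation r:
- two-sided family-wise error = 1 − P(|Z1| < 1.96, |Z2| < 1.96); at r = 0 this is 1 − 0.95² = 0.0975;
- false claim of benefit = 1 − P(Z1 < 1.96, Z2 < 1.96); at r = 0 this is 1 − 0.975² = 0.0494, against 0.025 for one endpoint.

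**3. Both must succeed, each at 0.05.** Alpha is controlled. Give each statistic mean 1.96 + 0.842 (80% power alone). Power = P(Z1 > 1.96, Z2 > 1.96); at r = 0 this is 0.80² = 0.64.

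**4. Holm.** The smaller p-value is tested at 0.025 (critical value 2.241), and the other at 0.05 if that succeeds.
- At least one claim: P(Z1 > 2.241 or Z2 > 2.241).
- Per endpoint: P(Z1 > 2.241) + P(1.96 < Z1 < 2.241, Z2 > 2.241).

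| r | Either: two-sided error | Either: false benefit | Both: power | Holm: at least one | Holm: per endpoint |
|---|---|---|---|---|---|
| 0 | 9.75% | 4.9% | 64.0% | 91.7% | 77.5% |
| 0.5 | 9.1% | 4.5% | 68.7% | 85.3% | 76.5% |
| 0.8 | 7.8% | 3.9% | 72.9% | 79.9% | 75.6% |
| 0.9 | 7.0% | 3.5% | 75.0% | 77.4% | 75.1% |

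**5. Unequal rates.** Suppose the second definition were 15% versus 5% (assumed). Its own power at 75 per arm is 53.3%. At r = 0, 0.5, 0.8 and 0.9, power to win both is 42.6%, 48.4%, 52.0% and 53.0%. Holm power for at least one claim is 83.4%, 76.7%, 72.7% and 71.6%.

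**6. If Fisher is used.** Its actual size for one endpoint at a 20% rate in both arms is 3.1%. In a simulation of 100,000 trials with correlated binary endpoints, null rate 20% and observed statistic correlation from 0 to 0.83, the either-wins error was 5.9% falling to 4.9%. Both-win power at 20% versus 5% was 58% to 69%. At these rates about 75 × 0.125 = 9.4 events per arm are expected, so chi-square would usually be chosen under a conventional expected-count cut-off of 5. That cut-off is an assumption; the SAP gives none.

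**The case against.** The strongest reply is that only one endpoint is meant. The hypothesis and the sample size speak of a single RAS, and the objective can be read as one event: spasm that is clinical and also confirmed by ultrasound. On that reading there is no multiplicity. This is plausible, and it stands as a possible meaning. But Protocol 7 numbers two primary endpoints and does not define the joint event, and SAP 3 does not tie 20% versus 5% to it. The passages would still need reconciling.

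Three further points stand and limit the size of the concern:
- The alpha inflation depends on the test. With Fisher, which SAP 4 allows, the error stays close to 5%.
- The hypothesis is directional, and about half of the two-sided error is false harm. False claims of benefit reach 4.9% at most, against 2.5% for one endpoint.
- Correlation reduces the either-wins error, though it is still 7.0% with chi-square at r = 0.9.

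A reader might also infer from the 4% to 51% range in Protocol 1 that the two definitions have different rates. That range covers RAS overall and is not split by definition. It shows that the rate is uncertain, and no more. The 15% versus 5% case is therefore only an illustration.

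**Conclusion.** The concern holds in this form: the plan names two primary endpoints, sizes one unlabelled RAS, and gives no rule linking them, so alpha 0.05 and about 80% power are delivered together only for one endpoint tested once. At 20% versus 5% on both and correlation 0 to 0.9 (both assumed), an either-wins rule with chi-square has 9.75% to 7.0% two-sided error, and a both-must-win rule has 64% to 75% power. The latter falls to 43% to 53% if the second definition were 15% versus 5%.

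Two stronger readings are not supported. A reader might infer that the trial is too small, but SAP 3's figure reproduces to within one participant per arm for a single endpoint. A reader might also infer that the success criterion was chosen with results in hand, because SAP 4 and SAP 5 describe the regression and the completion of all 150 participants as already done. That wording raises the question of what was known, but it does not show that outcomes had been seen by arm.

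**What to change.** In Protocol 7 and SAP 1, 3 and 4, state which definition 20% versus 5% describes, and date the change. What follows depends on what was known at that date.

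- **Outcomes not yet known.** Make that definition the single primary at two-sided 0.05, and test the other at 0.05 only if the first is significant. If the joint event is meant, define it in Protocol 7 as the primary and tie 20% versus 5% to it. Family-wise error stays at 0.05, with about 80% power for the primary claim. Cost: wording only, no added participants, but the second endpoint cannot support a claim alone.
- **Outcomes already known.** Do not choose a primary now. Report both endpoints with Holm-adjusted p-values and disclose that the rule was set post hoc. No wording restores pre-specification. At equal rates, Holm leaves per-endpoint power of about 75% to 78% and 92% to 77% for at least one claim. The latter is 83% to 72% if the second endpoint is 15% versus 5% (assumed).

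### Must the SAP add a between-arm estimate with confidence interval, and a PCI adjustment, for contrast volume, fluoroscopy time and radiation dose?

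*Combined protocol and SAP*

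**What the plan says.** SAP section 1 lists three continuous secondary objectives: "To compare fluoroscopy time (minutes", "To compare contrast volume (mL" and "To compare the radiation dose" (the last as DAP). Under Descriptive Statistics, SAP section 4 summarises each arm by mean and "SD if normally distributed; median (IQR) if not". Under Comparative Analyses it applies Shapiro–Wilk and then the test in "t-test (parametric), Mann–Whitney U test (non-parametric", judged at a two-tailed 0.05. Protocol section 8 says the same more briefly.

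The only interval in the plan belongs to the logistic regression for predictors of spasm: "Results presented as odds ratios (OR) with 95% confidence intervals (CI".

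Protocol section 6 allows both procedure types in the same trial: "PCI performed if indicated, with additional weight-adjusted heparin". SAP section 6 plans no subgroup analysis, so PCI and diagnostic cases are analysed together. The trial is sized on spasm alone (SAP section 3): "RAS incidence 20% in placebo group vs. 5% in verapamil group", 75 per arm.

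**The concern.** Three of the four secondary endpoints would be reported as two per-arm summaries and a p-value. None has a stated SD, target difference or power. If verapamil helps these endpoints only by preventing spasm, the benefit is spread over all patients while only 15 in 100 change status, so p > 0.05 would be common even with a real benefit. Without an interval, a reader could take that as no effect. A PCI is likely to raise all three measurements, so pooling puts extra variation into the comparison and makes it less precise. The secondary conclusions would be at stake; the primary spasm comparison and the sample size would not.

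**Working it through.** **1. The plan's own figure.** Inputs from SAP section 3: 20% vs 5%, two-sided alpha 0.05, power 80%. With the pooled two-proportion formula, the mean rate is 0.125 and

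n = [1.96·√(2·0.125·0.875) + 0.842·√(0.2·0.8 + 0.05·0.95)]² / 0.15² = (0.917 + 0.383)² / 0.0225 ≈ 75.1, so 76 per arm.

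At 75 per arm the power is 79.9%. The stated 75 per arm is reproduced, but it concerns spasm only.

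**2. Precision for a continuous endpoint at 75 per arm** (in SD units, no clinical assumption).
- 95% half-width: t(0.975; 148 df)·√(2/75) = 1.976·0.1633 = 0.32 SD.
- Difference detectable with 80% power: (1.960 + 0.842)·0.1633 = 0.46 SD.
- Power = Φ(δ/0.1633 − 1.96): 23% at 0.2 SD, 45% at 0.3 SD, 69% at 0.4 SD.

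A non-significant test is therefore compatible with a moderate true difference.

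**3. Dilution through spasm.** If each spasm multiplies the value by m (assumed; the documents give no figure), the ratio of geometric means is m^(−0.15): 0.94 for m = 1.5, 0.90 for m = 2, 0.85 for m = 3. Simulations with log-normal data, 75 per arm and an assumed within-type CV of 0.5, over PCI shares of 10% to 50% and PCI effects of 1.5- to 3-fold, gave Mann–Whitney power of 8% to 30%. A PCI-adjusted log-scale model gave 11% to 40%. These results depend on the CV:
- At CV 0.3, adjusted power reached about 59%, the raw t-test about 63%, and Mann–Whitney at most 34%.
- At CV 0.8, Mann–Whitney gave 7% to 21% and the adjusted model 7% to 26%.

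Low power is thus the usual result for Mann–Whitney, but not for every planned test under every assumption. An interval would describe the imprecision; it would not change the power.

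**4. What pooling PCI costs.** With PCI share p and PCI multiplier k (both assumed), the 95% interval for the ratio is the estimate multiplied and divided by

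exp{1.96·√(2·[s² + p(1−p)(ln k)²]/75)}, where s² = ln(1 + CV²).

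At CV 0.5, s² = 0.223, and with PCI adjusted for the factor is 1.163. Unadjusted:

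| PCI effect | p = 0.10 | p = 0.50 |
|---|---|---|
| 1.5-fold | 1.169 | 1.179 |
| 2-fold | 1.180 | 1.206 |
| 3-fold | 1.202 | 1.261 |

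The gain from adjustment is negligible at 1.5-fold and worthwhile only at the upper end.

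**5. What adjusting for PCI costs.** PCI comes after randomisation, and spasm may prevent it. Take p = 0.50, k = 3, m = 2, and let spasm stop every indicated PCI.
- PCI shares: placebo 0.5·0.80 = 0.400; verapamil 0.5·0.95 = 0.475.
- Unadjusted log ratio: −0.15·ln 2 + 0.075·ln 3 = −0.104 + 0.082 = −0.022, a ratio of 0.98.
- Adjusted: among PCI cases there is no spasm, so the arm effect is 0. Among the rest, spasm is 0.20/0.60 = 0.333 vs 0.05/0.525 = 0.095, giving −0.238·ln 2 = −0.165. The stratum weights are 0.4·0.475/0.875 = 0.217 and 0.6·0.525/1.125 = 0.280. The weighted mean is 0.280·(−0.165)/0.497 = −0.093, a ratio of 0.91.

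The adjusted model would show a benefit that the randomised comparison of all patients does not.

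**6. Validity.** Simulated null rejection rates at CV 0.5 were 4.2% to 5.8% for Mann–Whitney and 4.4% to 5.2% for the raw t-test.

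**7. Fit of a ratio to the planned tests.** A geometric mean ratio is the effect measure of neither planned test. Its interval and the Mann–Whitney p-value disagreed on significance in 2% to 11% of trials at CV 0.5, and in up to about 22% at CV 0.3.

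**The case for a change.** The strongest case for a change is that it is cheap and the benefit is real. One line of output per endpoint would show, for example, a ratio of 0.90 with an interval of 0.90/1.188 = 0.76 to 0.90·1.188 = 1.07 (spasm effect 2-fold, PCI share 10%, PCI effect 1.5-fold), which plainly does not exclude a useful benefit. Where data are normal, a reader can rebuild the interval from mean, SD and 75 per arm; where the SAP reports medians with IQR, the reader cannot do so exactly. The omission is also wider than these three endpoints. Procedural success and both spasm endpoints have only counts, percentages and a chi-square or Fisher test, and the logistic model in SAP section 4 does not name treatment arm among its variables.

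All of this stands as a description of the text, and estimates with intervals are good reporting practice. It does not show that following the plan gives a wrong or misleading result. The plan has no rule that reads p > 0.05 as no effect, makes no claim of power for these endpoints, and does not prevent an interval from being reported. The PCI part carries less weight. Its size rests wholly on assumed values, the covariate is measured after randomisation, and the documents do not say whether PCI status is recorded for analysis. Comparing all randomised patients is the correct intention-to-treat contrast, not a fault.

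**Conclusion.** No change to the plan is called for. SAP section 4 does leave out a between-arm estimate and interval, but this is missing reporting detail around valid tests, and an analyst can fill it in the ordinary way with a measure that suits whichever test is used. The precision involved is a half-width of 0.32 SD at 75 per arm, which follows from the sample size whether or not the interval is printed. Adjusting for PCI is at best a trade-off: an interval factor of 1.16 instead of 1.17 to 1.26 at an assumed CV of 0.5, against a possible shift of the ratio from 0.98 to 0.91. The power figures depend on an assumed CV, PCI share, PCI effect and spasm effect, and they vary too much with the CV to support a firm statement. SAP section 5 records that all 150 patients completed, so a new analysis chosen after the outcomes were seen would be post hoc. The primary spasm comparison and the stated sample size are unaffected.

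### With about 19 expected RAS events, the logistic regression in SAP section 4 is too thin for claims of independent prediction, and odds ratios that reach significance would be overstated

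*Combined protocol and SAP*

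**What the plan says.** Under Regression Analyses, SAP section 4 says "Logistic regression was performed to identify independent predictors of RAS". The candidate list is "Variables considered: age, sex, comorbidities, procedural factors". Results are to be shown as odds ratios with 95% confidence intervals, and the threshold is general: "Two-tailed $p < 0.05$ is considered statistically significant". Protocol section 8 adds only that logistic regression will be used for predictors.

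Neither document lists the individual comorbidities or procedural factors. Neither states the number of terms, a selection rule, a cap on model size, a penalised estimator, a multiplicity adjustment or an exploratory label. They do not say whether the treatment arm is in the model. They also do not say which of the two primary RAS endpoints in Protocol section 7 (clinical or ultrasonographic) is the outcome.

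The event count is not stated, but it follows from SAP section 3: "Assumptions: RAS incidence 20% in placebo group vs. 5% in verapamil group", with 75 participants per arm.

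**The concern.** The information in a logistic model is governed by the number of events, not the number of patients. Two of the four candidate groups are plural and open-ended, so the model could grow well beyond four terms on fewer than 20 events. No penalised method is named, so the natural reading is ordinary maximum likelihood. With so few events per coefficient, that estimator is biased away from the null and sometimes has no finite solution. Testing each candidate at 0.05 also lets chance findings accumulate.

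At stake is what the trial reports about who develops spasm. A covariate could be presented as an independent risk factor when it is not one, or a real but modest association could be reported at about twice its size. If the arm is in the model, the adjusted verapamil effect would be exaggerated too. SAP section 4 mentions odds ratios and confidence intervals only for this regression, so readers may give these estimates more weight than they can bear.

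**Working it through.** **Inputs.** From SAP section 3: 20% versus 5%, 75 per arm, 80% power, two-sided alpha 0.05. From SAP section 4: four candidate groups, tested at 0.05. The number of candidates, k, is not given, so it is an assumption shown over a range.

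**1. The plan's own sample size.** With the pooled-variance formula and mean rate 0.125:
n = [1.960 × √(2 × 0.125 × 0.875) + 0.842 × √(0.20 × 0.80 + 0.05 × 0.95)]² / 0.15² ≈ 75.1 per arm, or 76 rounded up (152 in total). Power at 75 per arm is 79.9%. The stated 150 is reproduced to within two patients, so the rates can be taken at face value.

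**2. Expected events.** 75 × 0.20 + 75 × 0.05 = 15 + 3.75 = 18.75. The 95% binomial range is 11 to 27.

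**3. Events per coefficient and false predictors.** If no candidate is a real predictor and candidates are independent, the chance of at least one p < 0.05 is 1 − 0.95^k. The simulated column comes from repeated runs of 150-patient trials at the design rates, with the arm in the model, null covariates and maximum-likelihood fits.

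| k (assumed) | 18.75 / k | 18.75 / (k + 1), arm added | 1 − 0.95^k | Simulated |
|---|---|---|---|---|
| 4 | 4.7 | 3.75 | 18.5% | 14% to 17.5% |
| 6 | 3.1 | 2.7 | 26.5% | 21% to 25% |
| 8 | 2.3 | 2.1 | 33.7% | 30% to 34% |
| 10 | 1.9 | 1.7 | 40.1% | 36% to 40% |

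The formula first passes one half at k = 14 (1 − 0.95^14 = 51%).

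**4. Size of the odds ratios that would be reported.** In 3,000 simulated trials per setting, with one third of covariates continuous and the rest binary at 30% prevalence, a binary covariate with a true odds ratio of 2 was significant in only about 27% of trials. When it was significant, its median odds ratio was 4.1 with 6 candidates and 4.6 with 10. Over all trials the average was 2.1 to 2.2, so the overstatement comes mainly from reporting what crosses the threshold. A null binary covariate that reached significance had a median odds ratio, away from 1, of 3.8 (4 candidates) to 4.5 (10 candidates).

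**5. The arm, if included.** The true log odds ratio is ln(0.05/0.95) − ln(0.20/0.80) = −2.944 + 1.386 = −1.558. Maximum likelihood averaged −1.69 with 4 candidates and −1.79 with 10. On the odds-ratio scale that is about 0.18 to 0.17 against a true 0.21. Firth-penalised fits gave about −1.54 to −1.57.

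**6. Fits with no finite solution.** About 2% to 4% with the covariates above, and about 16% to 18% if one candidate is a comorbidity with 10% prevalence. Most of the latter is direct arithmetic: no carrier has an event with probability (1 − 0.10 × 0.20)^75 × (1 − 0.10 × 0.05)^75 = 0.220 × 0.687 = 15%. Firth fits did not fail.

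**The case against.** The strongest reply is that this is a supporting analysis whose risks are easily overstated. Several parts of that reply stand.

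- **False predictors.** A reader might infer that the plan will probably report a false risk factor. The figures do not support that: the chance stays below one half until about 14 independent candidates, and the SAP gives no count.
- **Failed fits.** A reader might attribute a failure rate near 16% to a long candidate list. That rate comes from one assumed rare comorbidity. It is already 15.5% to 17.5% with only two candidates, and the documents give no prevalence for any comorbidity.
- **The arm's bias.** The arm is not in SAP section 4's list, so its exaggeration is conditional on including it. Nor is the covariate list the whole cause: with the arm alone, maximum likelihood already averages about −1.64 among finite fits, because the verapamil arm expects only 3.75 events. Firth with all 10 candidates gives about −1.55. The penalty removes the bias, so the case for a short list rests on false predictors and overstated significant findings.
- **The event count.** SAP section 3 does not say which RAS endpoint its rates describe. Applied uniformly to 150 patients, the 4% to 51% range in Protocol section 1 would give 6 to 77 events, and the upper end would ease the problem.
- **Reach.** Finding predictors is not a stated objective. The arms are compared by chi-square or Fisher's exact test, and nothing here touches that result.

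What does not stand is the suggestion that labelling alone would be enough. A plan should work at its own design rates. At those rates the significant odds ratios are overstated at every model size examined, and SAP section 6 plans no sensitivity analysis that could expose an unstable model.

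**Conclusion.** The concern holds for the regression and should be fixed, but it does not threaten the primary comparison. The event count and the events per coefficient follow directly from SAP section 3. The firmest consequence is overstatement: a real odds ratio of 2 would appear at about 4 to 5 when declared significant. False predictors are a material risk whose size depends on the unstated number of candidates. Bias in the verapamil estimate applies only if the arm is modelled, and the frequency of failed fits depends heavily on covariate prevalence. The simulated figures assume independent covariates and the design rates; correlated candidates, data-driven selection or modelling both RAS endpoints would change them.

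**What to change.** Replace the two lines in SAP section 4 that give the purpose of the regression and its variables with text such as:

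> Firth-penalised logistic regression will be fitted for [clinical or ultrasonographic RAS, to be named], with randomized arm and a short fixed list of pre-named baseline variables (for example age and sex). Other comorbidities and procedural factors will be tabulated by RAS status without p-values. The analysis is exploratory, and results will be described as associations.

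Procedural factors should stay out of this model. They arise after randomization and may follow from spasm: Protocol section 1 itself says spasm can cause technical difficulty and procedural failure. Age and sex are an example, chosen only because the SAP already lists them. What matters is that the list is short, fixed in advance and sized to the expected events.

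SAP section 7 names only SPSS 25.0, so add the software used for the Firth fit (R or an SPSS extension).

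The cost is SAP wording and minor software work, with no extra patients or data. The downside is that fewer variables can be claimed as predictors.
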